4. DATA HANDLING DEFINITIONS AND CONVENTIONS

4.1. Scheduled Study Evaluations and Study Periods

4.1.1. Day 1

Day 1 is the date of first dose of itacitinib/placebo in the treatment phase.

4.1.2. Study Day

If a visit/reporting date is on or after Day 1, then the study day at the visit/reporting date will be calculated as

$$\text{Day \#} = (\text{Visit/Reporting Date} - \text{Day 1 date} + 1).$$

If the visit/reporting date is before Day 1, then the study day at the visit/reporting date will be calculated as

$$\text{Day \#} = (\text{Visit/Reporting Date} - \text{Day 1 date}).$$

A study day of -1 indicates 1 day before Day 1.

4.1.3. Baseline Value

Baseline is the last nonmissing measurement obtained before or on the first day of itacitinib or placebo administration (in terms of date and time, if available).

4.1.4. Retreatment Day 1

Retreatment Day 1 is the date of first dose of itacitinib in the retreatment phase.

4.1.5. Analysis Visit Definition

In order to summarize data collected over time (including unscheduled visits and EOT visit), the following general rule will be applied in creating analysis visits:

- Step 1: The EOT assessment will be assigned to the next available scheduled assessment if it is measured within 3 days of the target day of next scheduled visit. For example, if a subject has an EOT assessment after scheduled visit Day 21, and the next scheduled visit is the Day 28 visit, then the assessment at EOT will be assigned to Analysis Visit Day 28 for this subject if they are assessed within 3 days of the target day of next scheduled visit.
- Step 2: If the scheduled assessment is available (including mapped EOT assessments in Step 1), then the scheduled assessment should be used; otherwise, the first nonmissing unscheduled assessment should be used.

Note that laboratory data were not scheduled to be collected per protocol at the Day 180 visit but were collected in study execution to support GVHD staging.

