Contact IVRS	X	X					X				X	X		X	X	X		
Demography/disease history	X																	
Prior/concomitant medications	X	X												X	X	X		
Supportive care medications	X	X												X	X	X		
AE assessment	X	X												X	X	X		
Physical examination	X	X	X	X	X	X	X	X	X	X	X		X	X	X	X		
Vital signs	X	X	X	X	X	X	X	X	X	X	X		X	X	X	X		
ECOG PS	X	X	X	X	X	X	X	X	X	X	X		X	X	X	X		
12-lead ECG	X	As indicated												X				
aGVHD grading and response	X	X	X	X	X	X	X	X	X	X	X	X	X	X	X	X	X	
cGVHD assessment	X	As indicated												X	X	X	X	
Chimerism/graft failure assessment	X	As indicated																
PTLD assessment		As indicated												X	X	X	X	
Underlying disease relapse assessment		As indicated												X	X	X	X	X
Dispense study drug		X				X				X			X		X			
Study drug compliance		X				X				X			X	X	X			
Steroid dose monitoring	X	X												X	X			
Survival follow-up																		X
New aGVHD therapies																		X

ECG = electrocardiogram; I/E = inclusion/exclusion; PS = performance status; PTLD = post-transplant lymphoproliferative disorder.

^a A ± 3-day window is permitted to facilitate scheduling during the treatment phase.

^b After Day 56, visits will occur every 28 days and will include all Day 56 assessments.

^c The Day 365 visit will also serve as the regularly scheduled visit occurring every 28 days after Day 56 (ie, Day 364).

^d A second EOT should occur if the subject restarts itacitinib and subsequently discontinues treatment.

^e Retreatment assessments occur every 28 days ± 3 days.

^f 30 to 35 days after EOT.

^g Every 28 days ± 7 days, for participants who completed study treatment or discontinued early for reasons other than GVHD progression.

^h Every 8 weeks ± 7 days.

Table 4: Laboratory Assessments

Visit Day Item	Screening	Treatment ^a											EOT ^e	Retreatment ^f	GVHD Follow-Up	Safety Follow-Up ^g	
	-28 to -1	D1 ^b	D7	D14	D21	D28	D35	D42	D49	D56 ^c	D100	D180					D365 ^d
Chemistry panel	X	X	X	X	X	X	X	X	X	X	X		X	X	X	X ^h	X
Hematology	X	X	X	X	X	X	X	X	X	X	X		X	X	X		X
Hepatitis screening	X																
HIV screening	X																
Serum pregnancy test (childbearing females only)	X													X			
Urine pregnancy test ⁱ (childbearing females only)						X				X							
PK assessment ^j		X	X			X											

^a A ± 3-day window is permitted to facilitate scheduling during the treatment phase.
^b Day 1 laboratory assessments do not need to be repeated if screening assessments were performed within the preceding 7 days.

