7.2. Efficacy Hypotheses

The primary efficacy analysis is the comparison of ORR at Day 28 between the 2 treatment groups. The following statistical hypotheses will be tested to address the primary efficacy objective:

$$H_0: ORR_{itacitinib} = ORR_{pbo} \text{ versus } H_1: ORR_{itacitinib} > ORR_{pbo}$$

where $ORR_{itacitinib}$ and ORR_{pbo} are the ORRs at Day 28 in the itacitinib and placebo groups, respectively. The CMH chi-square test, stratified by the randomization stratification factor (ie, standard risk and high risk), will be used to compare ORR between the 2 treatment groups, at the 1-sided 2.5% level of significance.

For the primary efficacy analyses, Day 28 ORR, as well as ORR for scheduled visits at Days 14, 56, 100, and 180, if available, will be used; if a scheduled assessment is not available but an unscheduled visit is available (within 3 days of the scheduled date), then the unscheduled assessment closest to the scheduled date will be used.

For summary analyses over time, analysis visits are defined Section 4.1.5, where analysis visits will be used in both tables and figures. The listings will include all collected data from the eCRF regardless of whether the visits are scheduled or unscheduled.

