7.3.1. Primary Efficacy Analysis

7.3.1.1. Day 28 Overall Response Rate

The primary efficacy endpoint, ORR at Day 28 (ie, with either a CR, VGPR, or PR at Day 28 assessment or other response assessments within 3 days of Day 28, before start of new anti-GVHD therapy), will be analyzed using a stratified CMH test. Note that the EOT visit must be accounted for in the Day 28 ORR calculation, because when the EOT and Day 28 visits occur at the same time, per protocol, EOT will supersede the Day 28 visit. That is, if the EOT visit occurs when the Day 28 visit is planned, data from the EOT visit will be used in lieu of the Day 28 visit.

Responders ([CIBMTR 2009](#), [Harris et al 2016](#); refer to Protocol Appendix B):

- (CR) Complete response
- (VGPR) Very good partial response
- (PR) Partial response

Non-responders:

- (MR) Mixed response
- (PD) Progression of disease
- (NR) No response
- (NA) Not applicable
- Other
- Missing (primary reason)
 - Death prior to the Day 28 visit
 - Withdrawal from study prior to the Day 28 visit
 - Initiation of new anti-GVHD therapy prior to the Day 28 visit
 - Missing visit

Day 28 ORR will be summarized using descriptive statistics (N, %) by treatment group with 2-sided exact binomial 95% CIs. P-value, mean proportion difference, odds ratio, and 95% Wald confidence limits calculated from stratified CMH test will be also presented.

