8.1. General Considerations

All safety analyses will be conducted using the safety analysis set and summarized by actual treatment received on Day 1. Summary tables may be replaced with listings when appropriate. For instance, an AE frequency table may be replaced with a listing if it only contains a few unique PTs reported on relatively few subjects.

For summary analyses over time, analysis visits for laboratory assessments/vital signs/ECGs are defined in Section [4.1.5](#).

Listings will include all collected visits from the eCRF regardless of whether the visits are scheduled or unscheduled.

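### SAP 4.1.5 fills a missed visit with the first unscheduled value and sets no time window, so descriptive laboratory and vital-sign summaries can be mistimed by up to about four weeks from Day 56 on

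*SAP*

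**What the plan says.** SAP 4.1.5 gives a general two-step rule for analysis visits. Step 1 moves an end-of-treatment assessment to the next scheduled visit only "if it is measured within 3 days of the target day of next scheduled visit". Step 2 keeps the scheduled (or mapped end-of-treatment) assessment where there is one; "otherwise, the first nonmissing unscheduled assessment should be used". Step 2 gives no window, no starting point for counting and no end date.

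Response endpoints have their own rule. For ORR at Days 14, 28, 56, 100 and 180, SAP 7.2 accepts an unscheduled visit only within 3 days, and "then the unscheduled assessment closest to the scheduled date will be used". SAP 7.3.1.1 repeats the limit for the primary endpoint ("or other response assessments within 3 days of Day 28"), and SAP 7.4.4 attaches a window of 3 days either side to the term analysis visit for the other response days.

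Two sections send other output to 4.1.5. SAP 7.2 states: "For summary analyses over time, analysis visits are defined Section 4.1.5, where analysis visits will be used in both tables and figures". SAP 8.1 does the same for safety data: "For summary analyses over time, analysis visits for laboratory assessments/vital signs/ECGs are defined in Section" 4.1.5. SAP 8.4 plans line graphs over time for platelets, neutrophils, cholesterol and triglycerides by arm.

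**The concern.** The section that defines analysis visits is the only one that lets an unscheduled value in without a time limit, and it takes the first such value rather than the nearest. A value taken soon after one visit can therefore be reported under the next.

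The rule also cannot be programmed in one way only. It does not say whether first is counted from Day 1, from the previous visit or from some later point. Read literally, one early value could fill several missed visits.

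The values chosen are unlikely to be a random sample. Protocol 6.6 links unscheduled measurements to adverse events or other findings. Protocol 5.4.2 asks for weekly evaluation after an interruption for toxicity, and its Table 1 asks for repeat bilirubin tests and for count monitoring as clinically indicated. A by-visit mean or a point on a platelet graph could then reflect a toxicity episode some weeks before the visit named on the axis. If the arms differ in missed visits or extra tests, they are affected unequally.

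**Working it through.** **Inputs.** SAP Tables 3 and 4 give visits on Days 1, 7, 14, 21, 28, 35, 42, 49 and 56. A footnote to both tables adds: "After Day 56, visits will occur every 28 days and will include all Day 56 assessments". Days 100, 180 and 365 are also listed, and Day 365 stands in for Day 364. SAP 4.1.5 notes that laboratory data were not scheduled at Day 180, so the laboratory grid below omits that day.

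**Check of the grid.** 56 + 11 × 28 = 364, which agrees with the day stated in the footnote.

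**Assumption.** The substitute value lies strictly between the previous scheduled visit *p* and the next one *n*. The SAP does not say so; without this bound there is no maximum.

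**Formula.** For target day *t*, the largest early error is *t* − (*p* + 1) and the largest late error is (*n* − 1) − *t*.

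| Target | Previous, next | Early (days) | Late (days) |
|---|---|---|---|
| Day 7 | 1, 14 | 7 − 2 = 5 | 13 − 7 = 6 |
| Day 28 (same for Days 14 to 49) | 21, 35 | 28 − 22 = 6 | 34 − 28 = 6 |
| Day 56 | 49, 84 | 56 − 50 = 6 | 83 − 56 = 27 |
| Day 84 | 56, 100 | 84 − 57 = 27 | 99 − 84 = 15 |
| Day 100 | 84, 112 | 100 − 85 = 15 | 111 − 100 = 11 |
| Day 112 | 100, 140 | 112 − 101 = 11 | 139 − 112 = 27 |
| Day 140 | 112, 168 | 140 − 113 = 27 | 167 − 140 = 27 |
| Day 168 (laboratory) | 140, 196 | 168 − 141 = 27 | 195 − 168 = 27 |
| Day 336 | 308, 365 | 336 − 309 = 27 | 364 − 336 = 28 |

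Where Day 180 counts as a visit, the late error at Day 168 falls to 179 − 168 = 11, and Day 180 itself can be 180 − 169 = 11 days early or 195 − 180 = 15 days late. If neighbouring visits use their own 3-day scheduling windows, the maxima rise by 3 days: 9 in the weekly phase, and 30 (31 for Day 336) later. Under the SAP 7.2 rule the maximum is 3 days at every visit.

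**What taking the first value does.** Suppose the visit at the end of a 28-day gap is missed and weekly tests fell 7, 14 and 21 days after the previous visit. Step 2 takes the value from 28 − 7 = 21 days before target. The nearest is 28 − 21 = 7 days before, and a 3-day rule would leave the visit missing. More generally, if *k* tests are spread uniformly over the gap, the first falls on average 28/(*k* + 1) days in, which is 28 − 28/(*k* + 1) days before target: 14 for *k* = 1, 21 for *k* = 3, 24 for *k* = 6. Both *k* and the uniform spread are illustrative; the documents give no rate of missed visits or unscheduled tests.

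**The case against.** The strongest reply is that little depends on this rule, and most of that reply stands.

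- **A reader might infer that 4.1.5 contradicts 7.2.** It does not. SAP 7.2 confines the nearest-within-3-days rule to ORR and in its next paragraph sends summaries over time to 4.1.5. The scopes are separate. What remains is an inconsistency of convention, plus loose wording: 7.4.4 treats a 3-day window as part of an analysis visit, while 4.1.5 gives none for unscheduled values.
- **A reader might infer that response data are mistimed by four weeks.** The ORR endpoints are limited to 3 days in three places. A descriptive by-visit response display, if one is planned, could use a different assessment from the ORR at the same visit, but near Day 28 the error is about 6 days. Most efficacy table titles in SAP Appendix B are absent from the text available, so such a display cannot be confirmed.
- **A reader might infer that all safety output is exposed.** SAP 8.1 refers only to summaries over time. The shift tables in 8.4 use the worst postbaseline value, listings show every collected visit, and cytopenias are also summarised as adverse events under 8.3. SAP 8.1 names ECGs, but Protocol 7.5.5 requires them only at screening and end of treatment, and SAP 8.6 summarises them at those points, so there is almost nothing for the rule to act on.
- **A reader might infer that off-drug values will enter on-treatment graphs.** SAP 8.4 limits the line graphs to the treatment phase, and Protocol 6.2 ends that period at permanent discontinuation. This answers the point for the graphs. Section 4.1.5 still has no end date of its own.
- **A reader might infer a bias for or against itacitinib.** No direction can be derived, and no hypothesis test uses these summaries.

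The missing window itself is not answered by any other section.

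**Conclusion.** The point holds for descriptive by-visit summaries only. Step 2 of SAP 4.1.5, applied as written, can put laboratory and vital-sign values about 6 days off target in the weekly phase and up to 27 to 28 days off at visits from Day 56 on. Those figures assume that neighbouring scheduled visits bound the value. That testing outside the schedule is prompted by toxicity is plausible from the protocol but not shown, and how often Step 2 would be used is unknown.

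One feature could make its use routine. SAP 4.1.5 says Day 180 laboratory data were collected although not scheduled. If they were recorded as unscheduled, which the SAP does not say, Step 2 would govern them for many subjects.

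The trial's efficacy conclusions are not at risk. This is a cheap improvement.

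**What to change.** Replace Step 2 of SAP 4.1.5: if the scheduled or mapped end-of-treatment assessment is missing, use the unscheduled assessment closest to the target day within 3 days; otherwise the visit is missing. State that treatment-phase displays use only assessments made in the treatment phase, and align 4.1.5 with the use of the term analysis visit in 7.4.4. A line on how Day 180 laboratory values are assigned would remove the remaining doubt.

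Contiguous windows around each target would also settle the ambiguity and lose fewer values, at the price of larger timing errors. The 3-day rule is preferred because the SAP already uses it for response.

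The cost is a sentence or two in the SAP, one change to the dataset derivation, and a few more visits shown as missing in descriptive tables and graphs. ORR at Days 14, 28, 56, 100 and 180 does not change.

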4.1.6. Last Available Value

The last available value is the last nonmissing measurement obtained after starting study treatment.

4.1.7. Date of Last Contact

The date of last contact is defined at the subject level as the latest date of discontinuation, laboratory assessment, GVHD/ECOG assessment, vital sign, ECG, scheduled or unscheduled visit, and any available date in the clinical database showing that the subject is still alive prior to or on the clinical data cutoff date.

4.1.8. Handling of Missing and Incomplete Data

In general, values for missing data will not be imputed unless methods for handling missing data are specified in this section or relevant sections.

Partial disease/cancer diagnosis date will be handled as follows:

- If only the day is missing, then the imputed day will be the first of the month.
- If both the month and day are missing, then the imputed day and month will be 01 JAN.
- No imputation will be done if the date is completely missing.

Missing date of last dose in the treatment period will be handled as follows:

- If the date is completely missing, then the imputed date of the last dose will be date of EOS, date of death, date of clinical data cutoff, or retreatment Day 1 – 1, whichever is the earliest.

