### **5.5. Withdrawal of Subjects From Study Treatment**

The decision to discontinue study treatment will not constitute study completion (see Section 5.5.3). In the event that the decision is made to discontinue study treatment, the treatment period will be considered complete, and the follow-up period will begin.

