**If a subject is withdrawn from study treatment:**

- The study monitor or sponsor must be notified.
- The reason(s) for withdrawal must be documented in the subject's medical record and in the eCRF.
- The EOT visit should be performed.
- The date of the EOT visit should be registered in the IVRS.
- Subjects must be followed for safety until the time of the follow-up visit or until study drug–related toxicities resolve, return to baseline, or are deemed irreversible, whichever is longest.

If the subject discontinues study treatment and actively withdraws consent for collection of follow-up data (safety follow-up or disease assessment), then no additional data collection should occur; however, subjects will have the option of withdrawing consent for study treatment but continuing in the follow-up period of the study for safety/efficacy assessments.

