6.5. Exposure

For subjects in the safety analysis set, exposure to study drug will be summarized descriptively as follows:

- **Duration of treatment with study drug:**

Duration of treatment (days) = Date of last dose of study drug – Date of first dose of study drug + 1

- **Average daily dose of study drug:**

Average daily dose of study drug (mg/day) = [total actual study drug dose taken (mg)] / [duration of treatment with study drug]

Frequency distribution of itacitinib/placebo duration category (days) will be tabulated by concatenated intervals: Day 1 through Day 28, Day 29 through Day 100, Day 101 through Day 180, and > Day 180.

Similarly, duration of corticosteroid and average daily dose of corticosteroid before EOT as the background therapy will be summarized by treatment group. Frequency distribution of corticosteroid duration category (days) will be tabulated by concatenated intervals.

Frequency distribution of itacitinib/placebo dose modification in the treatment phase (ie, dose decreased due to toxicity, dose increased, dose tapered, dose temporarily interrupted and with previous dose resumed) will be tabulated by concatenated intervals: Day 1 through Day 28, Day 29 through Day 56, Day 57 through Day 84, Day 85 through Day 112, Day 112 through Day 140, Day 141 through Day 168, Day 169 through Day 196, Day 197 through Day 224, Day 225 through Day 252, Day 253 through Day 280, Day 281 through Day 308, Day 381 through Day 336, Day 337 through Day 365, and > Day 365.

In order to summarize corticosteroid use over time in the treatment phase, for days of interest Day X (ie, X = 14, 28, 56, 100, and 180, separately), average corticosteroid dose (mg/day) during the week ending on Day X, relative corticosteroid dose (%) during the week ending on Day X will be summarized by treatment group. Number and percentage of subjects ongoing with itacitinib/placebo and ongoing with corticosteroid on Day X respectively will be summarized by treatment group.

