8.2. Adverse Events

8.2.1. Adverse Event Definitions

A TEAE in the treatment phase is either an AE reported for the first time or worsening of a pre-existing condition after first dose of itacitinib/placebo and before or at 30 days after last dose in the treatment phase. Analysis of AEs will be limited to TEAEs that occur during the treatment phase, but data listings will include all AEs, regardless of their timing with regard to study treatment administration.

A TEAE in the retreatment phase is either an AE reported for the first time or worsening of a pre-existing condition on or after Day 1 of retreatment with itacitinib. Treatment-emergent AEs in the retreatment phase will be listed.

Adverse events will be tabulated by MedDRA PT and SOC. Severity of AEs will be described and graded using the NCI CTCAE v4.03 ([NCI 2010](#)). The CTCAE reporting guidelines and grading details are available on the Cancer Therapy Evaluation Program website.

A grading (severity) scale is provided for each AE term. If the toxicity is not included in the CTCAE v4.03 criteria, then it will be rated on a scale of 1 to 5 as follows: 1 = mild, 2 = moderate, 3 = severe, 4 = life-threatening, and 5 = fatal. All toxicities will be graded based on the worst level reached, not the level they may have reached if they had not been treated. When the intensity of an AE changes over time for a reporting period (eg, between visits), then each change in intensity will be reported as an AE until the event resolves.

The subset of AEs considered by the investigator to be related to study drug will be considered to be treatment-related TEAEs. If the investigator does not specify the relationship of the AE to study drug, then the AE will be considered to be treatment-related. The incidence of TEAEs and treatment-related TEAEs will be tabulated. Serious TEAEs will also be tabulated.

Any missing onset date, causality, or severity must be queried for resolution. Unresolved missing values will be handled according to the following rules:

- An unresolved missing causality will be considered treatment-related.
- An unresolved missing severity will be identified as an unknown severity.

For purposes of analysis, all AEs will be considered TEAEs unless the AE can unequivocally be defined as not treatment-emergent.

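### The rule for a completely missing last-dose date omits the end-of-treatment date, so it overstates exposure for subjects who stopped drug but stayed in follow-up

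*SAP*

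**What the plan says.** SAP 4.1.8 covers a last-dose date in the treatment period that is completely missing: "then the imputed date of the last dose will be date of EOS, date of death, date of clinical data cutoff", or the day before retreatment Day 1, "whichever is the earliest". EOT is not in the list, and nothing else in the SAP caps the imputed date at EOT. EOS is not defined in the SAP. I read it as end of study, because the abbreviation list defines EOT separately as end of treatment.

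The last-dose date is used in three places:

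- SAP 6.5, duration: "Duration of treatment (days) = Date of last dose of study drug" minus the date of first dose, plus 1. Duration is also tabulated in four categories: Days 1-28, 29-100, 101-180 and beyond Day 180.
- SAP 6.5, average dose: "Average daily dose of study drug (mg/day) = [total actual study drug dose taken (mg)] / [duration of treatment with study drug", with that duration as the denominator.
- SAP 8.2.1: a TEAE must start after the first dose and "before or at 30 days after last dose in the treatment phase".

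Protocol 5.5 keeps stopping drug apart from leaving the study: "The decision to discontinue study treatment will not constitute study completion". Protocol 5.5.2 provides for an EOT visit and adds: "The date of the EOT visit should be registered in the IVRS".

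**The concern.** An imputed last-dose date should be no later than the earliest date by which the subject is known to be off drug. For a subject who has discontinued, that date is normally EOT. The listed alternatives mark when the subject left the study, died, reached the cutoff or was re-treated, and any of these can come long after the last tablet.

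At stake is the accuracy of the descriptive exposure summaries and, to a lesser degree, of the TEAE window. The error runs one way: it lengthens exposure and dilutes average dose, and it does so most for subjects who stopped earliest.

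**Working it through.** The plan gives no figure for this rule, so there is none to reproduce. The check follows the imputed date through the SAP formulas.

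**How late the listed dates can be.** Under Protocol 6.5.2, subjects who completed treatment or stopped for reasons other than GVHD progression are seen every 28 days, up to 12 months from EOT or 24 months from Day 1, unless an earlier stopping event occurs. Under Protocol 6.5.3, survival contact continues until death, consent withdrawal or end of study. For a living subject in follow-up who is not re-treated, the earliest listed date is therefore usually the data cutoff.

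**Inputs.** Starting dose 200 mg once daily (Protocol 5.2.1.1). Assumptions: stop on Day 28 with EOT the same day, no dose changes, total dose taken summed from recorded doses only, subject alive and in follow-up at the cutoff, not re-treated, last-dose date completely missing.

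**Formulas.** With the first dose on Day 1, duration = imputed last-dose day. Excess = imputed day − 28. Average daily dose = (28 × 200) / duration = 5600 / duration. TEAE window end = imputed day + 30.

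| Imputed last dose | Duration (days) | Excess (days) | Category | Average dose (mg/day) | Window ends |
|---|---|---|---|---|---|
| EOT, Day 28 | 28 | 0 | Days 1-28 | 200 | Day 58 |
| Cutoff at Day 180 | 180 | 152 | Days 101-180 | 5600/180 = 31.1 | Day 210 |
| Cutoff at Day 324 | 324 | 296 | > Day 180 | 5600/324 = 17.3 | Day 354 |
| Cutoff at Day 365 | 365 | 337 | > Day 180 | 5600/365 = 15.3 | Day 395 |

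The Day 324 row uses the SAP's own cutoffs. Interim 1 was cut on 25 JUN 2018 and Interim 2 on 17 APR 2019, 296 days later. A subject among the first 112 who was at Day 28 on the first date was at Day 28 + 296 = Day 324 on the second.

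**Range over the stop day.** For stops on Days 14, 28, 56 and 100, the excess is 166, 152, 124 and 80 days with a Day 180 cutoff, and 351, 337, 309 and 265 days with a Day 365 cutoff.

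**Scale in an arm of 218.** Each affected subject raises mean duration by 152/218 = 0.7 days (Day 180 cutoff) to 296/218 = 1.4 days (Day 324 cutoff). The documents do not say how many subjects would be affected.

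**The case against.** **The trigger is narrow.** This stands. The rule applies only when the date is completely missing, and Protocol 5.5.2 makes the last-dose date an eCRF item at discontinuation. Including the data cutoff suggests that the rule was written mainly for subjects still on drug, for whom it works. Nothing in the documents shows that any discontinued subject lacks the date.

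**End of study might fall near EOT.** Protocol 5.5.2 also says that a subject who permanently stops study drug leaves the study. Read alone, that would make EOS a good stand-in for EOT. It conflicts with Protocol 5.5, 5.5.3 and 6.5, which keep such subjects in follow-up. If it did hold, adding EOT would do no harm.

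**Late events and deaths.** A reader might infer that events and deaths long after stopping drug will be tabulated as treatment-emergent. The documents do not support that as a general consequence, because an event must first be collected as an adverse event. Protocol 8.1.2 requires monitoring for new events for at least 30 days after the last dose, and Protocol 6.5.1 puts the safety visit 30 to 35 days after EOT. Protocol 6.5.3 contacts ask about survival and new GVHD therapy, not adverse events. Some late capture is possible: Protocol 6.5.1 extends reporting until toxicities resolve, and Protocol 8.3.2 requires serious events to the last study visit, yet limits those beyond 30 days to suspected drug-related ones. The tables in SAP 8.2.2 are counts and percentages of subjects, so no exposure-time denominator is distorted. SAP 8.2.1 already treats events as treatment-emergent unless they clearly are not.

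**Compliance.** A reader might also infer that compliance is distorted. SAP 6.6 defines it as dose taken over dose prescribed, and the last-dose date is in neither term directly. That claim is not established.

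**Conclusion.** The rule is wrong as written for subjects who discontinued drug and remain in follow-up, and right for subjects still on drug at the cutoff. For each affected subject, duration is overstated by the gap between last dose and imputed date, which is 80 to 351 days over the stop days and the Day 180 and Day 365 cutoffs examined. The duration category can be wrong, and average daily dose can fall to a small fraction of the dose taken. The TEAE window lengthens by the same gap, with limited effect on the tables.

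This rests on reading EOS as end of study and on recorded doses forming the numerator of average dose. How often the rule would be applied to a discontinued subject is unknown and probably low. A material shift in an arm's mean exposure, or an imbalance between arms, would need an assumed frequency that the documents do not anchor, so neither is claimed. No efficacy endpoint uses this date. The point is minor, and worth correcting because the correction is nearly free.

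**What to change.** In SAP 4.1.8, impute a completely missing last-dose date as the earliest of: the EOT or treatment discontinuation date where available, the EOS date, the date of death, the data cutoff, and retreatment Day 1 − 1. Spell out EOS in the abbreviation list.

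The cost is one phrase in the SAP and one term in the derivation. Subjects still on drug at the cutoff are unaffected, since they have no EOT date. The change does not help where neither an EOT nor a discontinuation date exists. Protocol 6.5.1 allows that the EOT visit may not be performed, so any remaining case should be queried with the site.
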